| 8.2.3 | ECG-12 lead | x | x | | x | x | x | x | x | x | x | x | x | x | x | x | x |
| Appendix 4 | Thyroid function tests | x | | | | | | | | | | | x | | | x | x |
| Appendix 4 | Pregnancy Test ^d | x | x | | | | | | | | | x | | x | x | x | x |
| Appendix 4 | HAV, HCV, HIV, HBV | x | | | | | | | | | | | | | | | |
| 5.1.2 | Alcohol Use History | x | | | | | | | | | | | | | | | |
| 5.1.2, Appendix 4 | Alcohol, cotinine, and drugs abuse testing | x | x | | | | | | | | | | | | | | |
| 4.3 | Admission to Unit | | x | | | | | | | | | | | | | | |
| 4.3 | Discharge from Unit | | | | | | | x | | | | | | | | | |
| 4.3 | Ambulatory Visit | | | | | | | x | x | x | x | x | x | x | x | x | x |
| 4.1 | Administration of Study Treatment | | | x | | | | | | | | | | | | | |
| 8.5 | RO7565020 PK Sample(Serum) - SC cohorts ^{e,f} | | | 4 ^g | x | x | x | x | x | x | x | x | x | x | x | x | x |
| 8.5 | RO7565020 PK Sample(Serum) - IV cohorts ^{e,f} | | | 5 ^h | x | x | x | x | x | x | x | x | x | x | x | x | x |
| 8.6 | Anti-Drug Antibody (ADA) ^f | | | x ⁱ | | | | | x | x | x | x | x | x | x | x | x |
| 8.7.4 | Cytokine/Cytokine profile and complement activation (SC5b-9) (serum) | | | 3 ^j | x | x | x | x | x | x | x | x | x | x | x | | |
| 8.3 | Adverse Events | | | | | | | | | x | | | | | | | |
| 6.5 | Previous and Concomitant Treatments | | | | | | | | | x | | | | | | | |

Table 1 Schedule of Activities – Part 1a (cont.)

Abbreviations: ADA = anti-drug antibody; AE = adverse event; AMA = antimitochondrial antibody; ANA = antinuclear antibody; ASMA = anti-smooth muscle antibody; a-TPO = anti-thyroid peroxidase; CRP = C-reactive protein; ECG = electrocardiogram; ET = early termination; HAV = hepatitis A virus; HBV = hepatitis B virus; HCV = hepatitis C virus; HIV = human immunodeficiency virus; IV = intravenous; PK = pharmacokinetic; SAE = serious adverse event; SC = subcutaneous.

- a. Weight and height will be collected during screening period and Day 1. Weight will be collected in the following visits except Day 2, Day 3, and Day 4.
- b. These assessments do not need to be repeated on Day –1, if screening tests sample collection performed within 7 days before dosing.

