Abbreviations: ADA = anti-drug antibody; AE = adverse event; AMA = antimitochondrial antibody; ANA = antinuclear antibody; ASMA = anti-smooth muscle antibody; a-TPO = anti-thyroid peroxidase; CRP = C-reactive protein; ECG = electrocardiogram; ET = early termination; HAV = hepatitis A virus; HBV = hepatitis B virus; HCV = hepatitis C virus; HIV = human immunodeficiency virus; PK = pharmacokinetic; SAE = serious adverse event.

- a. A period refers to the time between one dose of treatment and the start of the next. Up to 6 periods in total.
- b. Day 1 refers to the first day of each treatment period. Study day will be calculated on the basis of dosing frequency, e.g., if the dosing frequency is every 28 days, Day 1 of the 2nd treatment period will be Day 29 of the study; If the dosing frequency is every 56 days, Day 1 of the 2nd treatment period will be Day 57 of the study; If the dosing frequency is every 84 days, Day 1 of the 2nd period will be Day 85 of the study. From the second treatment period, for sentinel participants, the whole period can be advanced or delayed by 1 day (i.e., an additional ± 1 day visit window); for non-sentinel participants, the whole period can be advanced by 1 day or delayed by 3 days (i.e., an additional $-1/+3$ days visit window).
- c. Dose frequency will be determined by emerging Part 1a data. Some of these visits will not be needed depending on dose frequency, e.g., if the dose frequency is every 28 days, Day 29 and Day 57 visits will not be needed; if the dose frequency is every 56 days, Day 57 visit will not be needed.
- d. Weight and height will be collected during screening period and Day 1. Weight will be collected in the following visits except Day 2, Day 3, and Day 4.
- e. These assessments do not need to be repeated on Day –1, if screening tests sample collection performed within 7 days before dosing.
- f. Assessment and sample collection will be performed at predose.
- g. Vital signs assessments on dosing days: predose, 1 hour postdose, and 4 hours postdose.

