- h. This assessment will be needed for Day 1 of some intermediate treatment periods only, depending on dose frequency. The minimum testing frequency of this assessment during treatment period is every 12 weeks. Thus, e.g., if the dose frequency is every 28 days, this assessment will be needed for Day 1 of the 4th treatment period only; if the dose frequency is every 56 days or every 84 days, this assessment will be needed for Day 1 of every intermediate treatment period.
- i. For all women enrolled in the study, blood sample for determining β -human chorionic gonadotropin (HCG) at Screening. Urine pregnancy tests will be performed at specified subsequent visits. If a urine pregnancy test is positive, it must be confirmed by a blood pregnancy test. Pregnancy testing will also be performed whenever a menstrual cycle is missed or when pregnancy is otherwise suspected and according to local practice.
- j. This assessment will be needed for Day 1 of some intermediate treatment periods only, depending on dose frequency. The minimum testing frequency of this assessment during treatment period is every 8 weeks. Thus, e.g., if the dose frequency is every 28 days, this assessment will be needed for Day 1 of the 3rd and the 5th treatment period; if the dose frequency is every 56 days or every 84 days, this assessment will be needed for Day 1 of every intermediate treatment period.

Table 2 Schedule of Activities – Part 1b (cont.)

- k. All participants will stay at the clinic overnight on Day 1 after each dose. Optional overnight stay at the clinic on Day 2 and Day 3 in the first treatment period: participants can either stay at the clinic overnight or can be discharged after completion of the postdose assessments and return the next morning for the subsequent assessments, at the Investigator's discretion.
- l. Unscheduled PK sample may be collected according to Section 8.2.3 and Section 8.5, e.g., at the time of treatment discontinuation if an infusion-related AE (such as an injection-related reaction) is reported, or when clinical significant abnormal ECG, an SAE, a severe AE, an AE leading to dose interruption or delay of RO7565020 administration, or an accidental overdose is reported.
- m. After participants complete the scheduled visits, an additional ADA and PK sample may be collected depending on the emerging ADA data.

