| 8.2.3 | ECG-12 lead | x | | x ^f | x | x | x | x | x | x | x ^f | x | x | x | x | x | x | x | x | |
| 5.2.2, Appendix 4 | Immunology (ANA, AMA, ASMA, a-TPO) | x | | | | | | | | | | x ⁱ | | | | | | | | |
| 5.2.2, Appendix 4 | Thyroid function tests | x | | | | | | | | | | x ⁱ | | | | | | | | |
| 5.2.2, Appendix 4 | Pregnancy Test ^k | x | x | | | | | | | | x | x ⁱ | | | | | | | | x |
| 5.2.2, Appendix 4 | AFP | x | | | | | | | | | | x ^m | | | | | | | | |
| 5.2.2, Appendix 4 | Abdominal ultrasound | x | | | | | | | | | | x ^m | | | | | | | | |
| 5.2.1, 8.7.1 | HBV DNA quantitative | x | | x | | | | | | | | x ⁱ | | | | | | | | |
| 8.7.1 | HBsAg | x | | 3 ⁿ | x | x | x | x | x | x | x ^f | x | x | x | x | x | x | x | x | |
| 8.7.1 | HBV Serology (HBeAg, anti-HBs, anti-Hbe) ^o | x | | x ^f | x | x | x | x | x | x | x ^f | x | x | x | x | x | x | x | x | |
| 8.7.1 | HBV RNA ^o | | | x ^f | | x | x | | x | x ^f | | | x | x | x | x | x | x | x | |
| 8.7.1 | HBcRag ^o | | | x ^f | | x | x | | x | x ^f | | | x | x | x | x | x | x | x | |
| 8.7.1 | Total anti-HBc ^o | | | x ^f | | x | x | | x | x ^f | | | x | x | x | x | x | x | x | |
| 8.7.1 | Total HBsAg (post-dissociation of HBsAg:HBsAb complexes) ^o | | | 3 ⁿ | x | x | x | x | x | x | x ^f | x | x | x | x | x | x | x | x | |
| 8.7.1 | HBsAg isoforms ^o | | | x ^f | | x | x | | x | x ^f | | | x | x | x | x | x | x | x | |
| 8.7.2 | HBV genotype | x ^f | | | | | | | | | | | | | | | | | | |
| 8.7.3 | Viral Resistance | x ^f | | | | | | | | | | | | | | | | | | |
| 5.2.2 | Transient elastography(e.g., Fibroscan)/ARFI/MRI ^q | x | | | | | | | | | | | | | | | | | | |
| 5.2.2, Appendix 4 | HAV, HCV, HDV, HEV, HIV | x | | | | | | | | | | | | | | | | | | |
| 5.2.2 | Alcohol Use History | x | | | | | | | | | | | | | | | | | | |
| 5.2.2, Appendix 4 | Alcohol and drugs abuse testing | x | | x ^f | | | | | | | | | | | | | | | | |
| 4.3 | Admission to Unit ^{r,s} | | | x | | | | | | | | x | | | | | | | | |
| 4.3 | Discharge from Unit ^r | | | | x | | | | | | | x | | | | | | | | |
| 4.3 | Ambulatory Visit ^r | x | x | | | x | x | x | x | x | x | x | x | x | x | x | x | x | x | |
| 4.1 | Administration of Study Treatment | | | x | | | | | | | | x | | | | | | | | |
| 6.1 | NUC | x | | | | x | | | | | | | x | | | | | | | |
| 8.5 | RO7565020 PK Sample ^{t,u} | | | 4 ^v | x | x | x | x | x | x | x ^f | x | x | x | x | x | x | x | x | |

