| Part 1a (healthy participants) | 
 Cohort 1: 70 mg RO7565020 SC (starting dose) or placebo, single dose Cohort 2: 230 mg RO7565020 SC or placebo, single dose Cohort 3: 360 mg RO7565020 SC or placebo, single dose Cohort 4: 360 mg RO7565020 IV or placebo, single dose (over 2-hour infusion) Cohort 5: 900–1500 mg RO7565020 IV or placebo, single dose (over 2-hour infusion) Cohort 6 (PK bridging cohort): 360 mg RO7565020 SC or placebo, single dose | N/A |
| Part 1b (healthy participants) | 
 Multiple doses (3 to 6 doses depending on dosing frequency). Dose level and dosing frequency will be determined using Part 1a data | N/A |
| Part 2a (participants with CHB) | 
 Cohort 1: 70 mg RO7565020 SC (starting dose), single dose Cohort 2: 230 mg RO7565020 SC, single dose Cohort 3: 360 mg RO7565020 SC, single dose | NUC |
| Part 2b (participants with CHB) | 
 Cohort 1 (optional): 70 mg RO7565020 SC, single dose Cohort 2: 230 mg RO7565020 SC, single dose Cohort 3: 360 mg RO7565020 SC, single dose Cohort 4 (optional): 720 mg RO7565020 SC, single dose | NUC |

Table 6 Provisional Dose Regimens in Each Study Cohort (cont.)

| Study part | Study treatment | Background treatment |
|---------------------------------------|---|-----------------------------|
| Part 3 (participants with CHB) | 
Multiple doses (up to 6 doses depending on dosing frequency). Dose level and dosing frequency will be determined using Part 1 and Part 2 data | NUC |

Abbreviations: CHB = chronic hepatitis B; IV = intravenous; N/A = not applicable; NUC = nucleos(t)ide analogue; PD = pharmacodynamic; PK = pharmacokinetic; SC = subcutaneous.

Note: Depending on the evaluation of the safety and/or PK/PD data, the same dose may be repeated; the actual dose may be modified to a lower dose; or intermediate dose-escalation steps other than those anticipated above may be used at the discretion of the Investigator and the Sponsor.

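### Part 1b with 84-day dosing: Table 2 schedules no pregnancy test for 12 weeks after the first dose, against its own 8-week minimum

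*Combined protocol and SAP*

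**What the plan says.** Table 2 (Section 1.3) sets the Part 1b visits for a dosing interval still to be chosen. Its footnotes work through 28, 56 and 84 days.

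- **Footnote j**, attached to the pregnancy test on Day 1 of the intermediate periods, gives the rule: "The minimum testing frequency of this assessment during treatment period is every 8 weeks". Its worked example adds that "if the dose frequency is every 56 days or every 84 days, this assessment will be needed for Day 1 of every intermediate treatment period".
- **Footnote b** places the second dose: "If the dosing frequency is every 84 days, Day 1 of the 2nd period will be Day 85 of the study".
- **Footnote c** removes visits that a short interval makes redundant. At 28 days, Day 29 and Day 57 go. For the middle option, "if the dose frequency is every 56 days, Day 57 visit will not be needed". Neither visit is removed at 84 days.
- **Pregnancy row, screening to the end of the intermediate periods:** marks at screening, Day -1, intermediate Day 1 (predose) and intermediate Day 57. Every first-period visit from Day 1 to Day 57 is blank.
- **Pregnancy row, last period:** marks at Day 1 (predose) and Days 29, 85, 141, 197 and 253.
- **Footnote i** adds event-driven testing: "Pregnancy testing will also be performed whenever a menstrual cycle is missed", or on other suspicion of pregnancy, and according to local practice.

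Table 6 (Section 4.1) allows three to six doses in Part 1b, and Table 7 (Section 4.3) limits the treatment period to 169 days.

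**The concern.** The footnote and the grid disagree for one of the three intervals that the protocol names. A site following the grid at 84-day dosing would see women at first-period Day 57 and not test them, although eight weeks have passed since the first dose.

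The 84-day interval is a real option. Three doses on Days 1, 85 and 169 match both the smallest number of doses allowed and the longest treatment period allowed.

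What is at stake is how soon a pregnancy is found. RO7565020 is a first-in-human antibody modified for a longer half-life (Section 2.2.3). A pregnancy requires stopping study treatment (Section 7.1) and reporting to the sponsor within 24 hours of the investigator learning of it (Section 8.3.5). No endpoint, estimate or dose-escalation rule depends on this cell.

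**Working it through.** **Inputs.** Test marks come from the Table 2 pregnancy row, which has 18 cells under 18 visit headings up to the end of the intermediate periods. Dose days are 1, 1 + q, 1 + 2q and so on, where q is the interval in days (footnote b). The number of doses is capped at six and by the 169-day treatment period:

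- q = 28: six doses, the last on 1 + 5 × 28 = Day 141
- q = 56: four doses, the last on 1 + 3 × 56 = Day 169
- q = 84: three doses, the last on 1 + 2 × 84 = Day 169

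**Rule.** At most 8 × 7 = 56 days between scheduled tests. Days are nominal, without visit windows. The first gap is counted from the first dose, which the Day -1 test covers; counting from Day -1 itself adds one day to that gap in every schedule.

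**Test days.** At 28 days, footnote j tests periods 3 and 5 (Days 57 and 113), and the last period is tested on its Day 1. At 56 days, every later dosing day is tested. At 84 days, the single intermediate period is tested on its Day 1 (Day 85) and its Day 57 (85 + 56 = Day 141), and the last period on Day 169.

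| Interval | Dose days | Test days after first dose | Gaps (days) | Within 56? |
|---|---|---|---|---|
| 28 days | 1, 29, 57, 85, 113, 141 | 57, 113, 141 | 56, 56, 28 | Yes |
| 56 days | 1, 57, 113, 169 | 57, 113, 169 | 56, 56, 56 | Yes |
| 84 days | 1, 85, 169 | 85, 141, 169 | **84**, 56, 28 | First gap no |

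The 8-week figure is reproduced at 28 and 56 days. At 84 days the first gap is 85 − 1 = 84 days, or 12 weeks: an excess of 84 − 56 = 28 days. After the last dose the gaps are 28 days and then 56 days each, so nothing else fails.

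**Omission or intention?** Footnote c keeps a Day 57 visit only at 84-day dosing. The mark at intermediate Day 57 can therefore serve only that schedule, which shows that a mid-period test was thought necessary in an 84-day period. The first period lacks it. In Table 4 (Part 3) the pregnancy row has two adjacent marks, read as first-period Day 57 and intermediate Day 1. Table 1 (Part 1a) also has a test at Day 57.

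**The case against.** **The blank may be an extraction fault.** In the machine-read copy of Table 2, the PK row also has the right number of cells, yet its Day 1 samples sit under Day -1. A correct cell count therefore does not prove that a blank is real. This stands as a reason to look at the PDF. It does not remove the point: all four marks in the pregnancy row fall where the footnotes or plain sense put them, including the predose mark on intermediate Day 1.

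**The comparators are imperfect.** The Table 4 pregnancy row has two more cells than headings, and in neighbouring rows a predose mark lands in the Day 57 column. The Table 1 row goes from Day 57 to Day 141, itself an 84-day gap, though footnote j does not govern Part 1a. Both are fair. They make Tables 1 and 4 supporting evidence only; the conflict lies within Table 2.

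**Footnote j itself addresses 84-day dosing.** Its example asks for the test on Day 1 of each intermediate period, and the grid does that. But the example is offered as an illustration of the 8-week rule, and for the first period it gives 12 weeks. On that reading the footnote contradicts itself and still needs correcting.

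**The consequence is slight.** The predose test on Day 85 would stop the second dose, and a Day 57 test cannot undo exposure to the first. Highly effective contraception is required (Section 5.1.1), missed-cycle testing applies, and Section 8.11.5 allows unscheduled assessments. All of this stands and limits the severity. None of it supplies a scheduled test at eight weeks, because missed-cycle and unscheduled tests depend on an event or a clinical reason.

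**Conclusion.** The point holds, as a minor one. As the table reads, 84-day dosing in Part 1b leaves one breach of the protocol's own testing minimum: 84 days against 56, in the first treatment period only. A pregnancy in that period could be found up to four weeks later than the rule allows. No dose would be given without a test just before it.

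This rests on three conditions: Part 1b is run, the 84-day interval is chosen, and the first-period Day 57 cell is blank in the PDF as it is in the text read here. Only the women among 8 participants would be affected. Confidence is medium because of the third condition.

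**What to change.** Confirm the first-period Day 57 cell of the Table 2 pregnancy row in the PDF. If it is blank, mark a urine pregnancy test there, applicable when dosing is every 84 days, and extend the example in footnote j to mention it. Test days then become 57, 85, 141 and 169, with gaps of 56, 28, 56 and 28 days counted from the first dose, all within eight weeks.

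The cost is one mark in the table, a short addition to the footnote, and one urine test per woman at a visit that footnote c already keeps. It is best done before the Part 1b dosing interval is chosen, so that sites do not receive a grid and a footnote that disagree.

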2. INTRODUCTION

2.1 STUDY RATIONALE

Chronic hepatitis B (CHB) virus infection is a major global healthcare problem, with an estimated prevalence of 296 million people ([WHO 2022](#)). The current standard of care is either a possibly lifelong treatment with nucleos(t)ide analogues (NUCs) or interferon (IFN)- α preparations that, despite their poor safety and tolerability, provide in rare cases (~3%) a functional cure for patients (defined as the sustained loss of serum hepatitis B surface antigen [HBsAg] and hepatitis B virus [HBV] DNA; [Lok et al. 2017](#)).

RO7565020 is a human origin monoclonal antibody (mAb) being developed for the treatment of CHB. RO7565020 binds the "a-determinant" of the antigenic loop present in all forms of HBsAg and, as a potent HBsAg depleting agent, offers a potential to increase the functional cure rate or shorten the duration of treatment when given in combination with a direct acting antiviral and/or an immunomodulator for patients with CHB.

This first-in-human (FIH), multi-center, dose-escalation Phase I clinical study of RO7565020 is aiming to investigate the safety, tolerability, pharmacokinetics, pharmacodynamics, and preliminary antiviral responses following single and/or multiple doses of RO7565020 via SC injection and/or IV infusion in healthy participants and in virologically suppressed participants with CHB.

The scientific rationale for the study design is provided in Section [4.2](#).

2.2 BACKGROUND

2.2.1 Background on Chronic Hepatitis B

HBV infection is a major cause of both acute hepatitis and chronic liver disease including cirrhosis and hepatocellular carcinoma (HCC). WHO estimates that 296 million people were living with CHB infection in 2019, with 1.5 million new infections each year. In 2019, HBV infection resulted in an estimated 820,000 deaths, mostly from complications including cirrhosis and HCC ([WHO 2022](#)).

Persistence of HBV infection is a consequence of the presence of covalently closed circular DNA (cccDNA) in the nuclei of infected hepatocytes. Despite the advancement in the understanding of HBV disease biology, eradication of cccDNA (defined as disease cure) is not likely in the near future. Nevertheless, the sustained clearance of HBsAg has been shown to be protective against disease progression and development of HBV complications including cirrhosis, liver failure, and HCC. Accordingly, current drug development efforts aim to achieve functional cure of CHB (i.e., sustained loss of HBsAg and HBV DNA) with finite treatment regimens ([Lok et al. 2017](#)).

2.2.2 Currently Available Therapies

Currently, there are two therapeutic classes available for the treatment of CHB: subcutaneously (SC) administered IFN preparations (conventional or pegylated [PEG]-IFN- α) and orally administered NUCs (tenofovir, entecavir, adefovir, telbivudine, and lamivudine). After 1 year of treatment, both types of treatment can suppress circulating HBV DNA levels (virologic response 7%–94%), normalize serum liver transaminase enzymes (biochemical response 32%–83%), and induce hepatitis B e antigen (HBeAg) seroconversion in HBeAg-positive patients (serological response 10%–32%). Although these treatments reduce the risk of CHB sequelae, they are associated with very low rates of functional cure (HBsAg loss rates generally not exceeding 3% after 1 year of therapy) ([European Association for the Study of the Liver \[EASL\] 2017](#)).

Furthermore, the existing standard-of-care therapies have important limitations. For example, virologic relapse after treatment discontinuation is a major limitation of currently approved therapies, which rarely result in functional cure. IFN-based therapies have common adverse events (AEs) of flu-like symptoms and can be associated with treatment-limiting adverse effects (e.g., neutropenia, thrombocytopenia), while NUCs require long-term and possibly lifelong therapy in the majority of treated patients. Given these limitations, there is an unmet need for novel treatments of a finite duration that yield higher functional cure rates ([Liu et al. 2017](#); [Durantel and Zoulim 2016](#); [Lok et al. 2017](#); [Wang and Chen 2014](#)).

2.2.3 Background on RO7565020

RO7565020 is a human IgG1 mAb (anti-HBs neutralizing antibody Bc1.187) with a well characterized neonatal Fc receptor (FcRn) affinity-enhancing Fc mutation (M252Y/S254T/T256E; YTE) introduced to increase the half-life and enhance the pharmacokinetic (PK) properties. RO7565020 binds to the antigenic loop present in all forms of HBsAg (L-HBsAg, M-HBsAg, and S-HBsAg) and showed potent and cross-reactive neutralization against genotypes A, B, C, and D in vitro.

Sequential to a single dose of small interfering RNA (siRNA) surrogate, single dose RO7565020 treatment further reduced HBsAg level in the adeno-associated virus (AAV)-HBV mouse model from 3 log₁₀ IU/mL to close to undetectable levels (<0.2 log₁₀ IU/mL).

In addition, RO7565020 can mediate phagocytic cell uptake of HBsAg particles, suggesting that antibody-coated viral particles and/or infected hepatocytes could be eliminated in vivo by phagocytes such as Kupffer cells. The Fc receptor-dependent function of antibody-dependent cellular phagocytosis (ADCP) may also facilitate antigen presentation to antigen-specific T cells, which could stimulate host humoral and cellular immune responses, a phenomenon known as the vaccine-like effect.

A detailed description of the chemistry, pharmacology, nonclinical efficacy and safety of RO7565020 is provided in the [RO7565020 IB](#).

